9.11.2 Secondary Objective Assessment

The secondary objective assessment will establish whether the frequency of CGM-determined hypoglycemic episodes differs during 4 weeks of carvedilol treatment compared to baseline and compared to the placebo-treated control group.

Patients will wear a blinded CGM that is installed 14 days prior the first clamp study and the device will continue to be worn throughout the entire study. These CGMs will be calibrated using the provided Bayer Contour Next EZ[®] glucometer. During the first clamp study, the follow-up visit and the second clamp study, data from the CGM will be downloaded and saved onto a secure server and exported into an Excel format for analysis. We will identify the number hypoglycemic excursions during the intervention period and compare this to the number of hypoglycemic episodes encountered during the 7-day period before the first clamp study, the “baseline” period. Comparisons between treatment groups at baseline and following the intervention period, as well as differences from baseline within each treatment group will be made.

Analysis of the CGM data will emphasize the number of hypoglycemic episodes as well as the duration and depth of the hypoglycemic episodes. A single hypoglycemic episode is defined as a glucose reading <70 mg/dL, followed by a reading ≥ 70 mg/dL, lasting at least 15 minutes or at least two readings below 70mg/dL over 15 minutes. If there is less than 30 minutes between two registered episodes of hypoglycemia these are considered as one episode.

We will also evaluate the answers to the fear surveys to determine whether those patients who are treated with carvedilol have a reduction in their fear of hypoglycemia compared to those on placebo.

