9.8 Continuous Glucose Monitor (CGM) and Glucometer

A blinded continuous glucose monitor (CGM) will be placed after enrollment and continue until the end of the second hypoglycemic clamp study. At this time, the participants will also be issued a Bayer Contour Next EZ[®] glucometer which they will use to monitor their blood glucose for the duration of the study and also to calibrate the CGMs. Instructions on how to use the glucometer will be provided at this time.

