collected to measure glucose, HbA1c, hematocrit and hormones (glucagon, catecholamines, insulin, cortisol, growth hormone, pancreatic polypeptide). Blood samples collected for assessment of plasma glucose (1mL) during the clamping procedure will be aliquoted into heparin coated 1ml Eppendorf tubes to prevent coagulation and processed immediately in the YSI and/or Analox Instruments glucose analyzer. In addition, the participants will be asked to fill in questionnaires to assess their perception of hypoglycemic symptoms (Edinburgh Hypoglycemia Symptom Scale) and their fear of hypoglycemia. Subsequently, the subjects will be given KCl tablets (20-40mEq) to help maintain potassium levels during the clamping procedure. Once assessment of baseline parameters has been completed, constant insulin (2mU/kg/min) and variable 20% dextrose infusions will be started at -60 minutes to establish stable glucose levels of ~90mg/dl before gradually lowering plasma glucose levels in three steps from 90-65-55-45 mg/dl by gradually reducing the glucose infusion rate. Plasma glucose levels will be monitored from a 1ml blood sample every 5min using a YSI and/or Analox glucose analyzer. A second Analox Instruments glucose analyzer and glucometer will be kept on hand as a backup. It is important that the glucose levels NOT be communicated verbally during the clamping procedure as notification of declining glucose concentrations to the participant might trigger confounding (i.e. artificially higher) awareness scores or stress hormone responses. Each glycemic step will be held for 30 minutes, allowing enough time for blood collection (~30mL at each glycemic plateau) and completion of the Edinburgh questionnaire at each glycemic plateau. At each glycemic step, plasma hormones (glucagon, catecholamines, insulin, cortisol, growth hormone, pancreatic polypeptide) will be evaluated. The frequent assessment of hypoglycemia symptom scores allows us to identify the threshold at which hypoglycemic symptoms are first noticed by the subject. We chose glycemic targets of 55 and 45mg/dl as hypoglycemic symptoms generally first appear between 55-65mg/dl in hypoglycemia aware individuals. In contrast, symptoms may not manifest in hypoglycemia unaware patients until glucose levels reach 45mg/dl. Targets of 55 and 45mg/dl allow us to safely determine whether carvedilol treatment raises the glucose threshold at which symptoms are first detected (i.e. improving hypoglycemia awareness). No more than 500mL of blood will be collected throughout the entire clamping procedure which is equivalent to the volume of a single blood donation. After the clamp, the participant's glucose levels will be recovered to normal by stopping the insulin infusion and raising the glucose infusion rate. In addition, a meal will be provided to aid recovery. This first set of clamps will establish a baseline response in the participant prior to the start of the intervention phase of the study. **Dispersal of Intervention Drug:** At the end of the clamp procedure, the subjects will be supplied with either placebo or one of two different doses of carvedilol, 2.5mg or 3.125mg, along with instructions on how to take the medication. The research staff and participant will be blinded to the treatment being received. The initial dose will be taken on the day following the clamp. In addition, the participant will also receive a hypoglycemia log book along with instructions on how to document hypoglycemia incidences and whom to contact in case of medical concerns. Once the participant's blood glucose levels are stable and he/she is ready to be discharged, we will provide them with glucose tablets and we will cover the cost of transportation home as a precautionary measure.

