10 STATISTICAL CONSIDERATIONS

A total of 21 T1DM patients with impaired awareness of hypoglycemia will be sought for this study. For the dose response study, we plan to enroll 21 of these patients who will be randomized to either placebo (N=7) or carvedilol (2.5mg or 3.125mg twice daily; N=7 each).

In estimating the appropriate sample sizes required to yield adequate statistical power, assuming a Type II error rate (β) of no more than 20% for a given test and a Type I error rate of $\alpha=5\%$, we used the following: $\text{Power} \geq 1-\beta = 1-0.2 = 0.8$

Treatment effects will be analyzed using one- or two-way analysis of variance (ANOVA) for independent or repeated measures as appropriate, followed by suitable *post-hoc* analysis. Analyses will be performed using the GraphPad Prism[®] or SAS[®] suite of software. We will use a significance level of $\alpha<0.05$.

Primary variables:

- a) Symptom Scores (autonomous, neuroglycopenic and other symptoms of hypoglycemia)
- b) Counterregulatory Hormone Responses (glucagon, epinephrine, norepinephrine, growth hormone and cortisol levels)

Secondary variables:

- a) Frequency of hypoglycemia assessed by CGM.

The primary and secondary variables will be analyzed by the statistical approaches mentioned above.

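### Section 9.11.2 compares a 4-week CGM episode count with a 7-day count and gives no time unit; read literally, every arm shows about a four-fold rise from baseline with no drug effect

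*Combined protocol and SAP*

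**What the plan says.** In section 9.11.2 the quantity on the treatment side is the "number hypoglycemic excursions during the intervention period". For the baseline side, the stated plan is to "compare this to the number of hypoglycemic episodes encountered during the 7-day period before the first clamp study". The section plans comparisons between arms at baseline and after the intervention, and also states that "differences from baseline within each treatment group will be made". An episode needs readings below 70 mg/dL lasting at least 15 minutes, or "at least two readings below 70mg/dL over 15 minutes".

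Section 6.3 sets treatment at 28 days. Section 10 lists the secondary variable as "Frequency of hypoglycemia assessed by CGM" and assigns it the same one- or two-way ANOVA as everything else. Section 4.1 and the opening of 9.11.2 also speak of frequency. None of these places attaches a per-day or per-week unit, an exposure offset, a matched 7-day treatment window or a wear-time rule.

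Two further provisions bear on where the windows end. Under 9.8 the sensor will "continue until the end of the second hypoglycemic clamp study", and that clamp involves "gradually lowering plasma glucose levels in three steps from 90-65-55-45 mg/dl"; "Each glycemic step will be held for 30 minutes". Under 9.10 a clamp goes ahead only if the preceding 24 hours were free of readings below 75-80 mg/dL, and the second clamp follows the same procedure as the first.

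**The concern.** The one sentence that tells the analyst what to compute sets a number from about four weeks against a number from one week. An analyst who follows it obtains a difference driven by observation time. The within-arm change from baseline is a planned secondary result. On raw counts it would show hypoglycemia rising in all three arms, and a drug that truly reduced episodes could be reported with a rise from baseline. In a trial whose secondary aim is to show less hypoglycemia on carvedilol, that is a misleading result even though placebo would show it too.

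The open window limits matter for a smaller reason: they would remain open after conversion to a rate.

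**Working it through.** **Inputs.** Baseline window 7 days (9.11.2). Treatment window 28 days (6.3). Dosing days: first dose the day after clamp 1 (9.10) and last dose the day before clamp 2 (section 8, footnote 4), so 27 days if the clamps are 28 days apart. Seven participants per arm (4.3, section 10).

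The plan states no expected episode count, rate or fold change, so it has no figure of its own to reproduce here. The sample size of 21 comes without an effect size or SD, and nothing below depends on it.

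**1. Raw counts, no drug effect.** With a constant rate and complete wear, the expected ratio of counts is treatment days / baseline days.
- 28/7 = 4.0
- 27/7 = 3.86

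If wear were complete at baseline but only 90% or 70% on treatment (assumed), the ratio would be 28 × 0.9/7 = 3.6 or 28 × 0.7/7 = 2.8.

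**2. With a drug effect.**
- A halved rate gives 0.5 × 4.0 = 2.0, an apparent doubling.
- Equal counts need a true reduction of 1 − 7/28 = 75% (1 − 7/27 = 74% on 27 days).

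**3. What a within-arm test would show.** Simulation with 7 participants, 20,000 replicates and a paired t-test, assuming 2, 3 or 5 episodes per week. Section 2 gives 2-3 per week, but for symptomatic episodes, so these rates are illustrative. Counts were Poisson or overdispersed (gamma-Poisson, shape 2).

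| Comparison | Result |
|---|---|
| Raw counts, no effect: significant rise | 83-100% of replicates |
| Raw counts, true halving: significant rise | 33-82% |
| Weekly rate, no effect: significant | 4.7-5.3% |
| Raw change compared between two arms, no effect | 4.3-5.1% |

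The last row confirms that the artefact cancels between arms when exposure is equal.

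**4. Between arms with unequal exposure.** If one of 7 participants is removed at day *d* and the partial count is kept, the arm mean changes by (6 × 28 + *d*)/196 − 1.
- *d* = 7: 175/196 − 1 = −10.7%
- *d* = 21: 189/196 − 1 = −3.6%

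**5. Clamp 2, if it were counted.** The three targets below 70 mg/dL last 3 × 30 = 90 minutes, which meets the 9.11.2 episode definition once. One episode in 28 days adds 1/4 = 0.25 per 7 days to the treatment side only, since the baseline ends before clamp 1. In time terms it is 90/(28 × 1440) = 0.22% of the period.

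**6. The pre-clamp 24 hours.** The 75-80 mg/dL screen is stricter than the 70 mg/dL episode limit, so a day that passes contains no episode. Assume that the other days run at the usual rate.
- If only the baseline runs up to its clamp, the null rate ratio is 1/(6/7) = 1.167.
- If both windows run up to their clamps, it is (27/28)/(6/7) = 1.125.

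The same rule applies before both clamps, but one day is a larger share of 7 than of 28.

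**The case against.** The strongest reply is that *frequency*, used in 4.1, 9.11.2 and section 10, naturally means a rate. A competent analyst would divide by time, and a four-fold rise on placebo would expose the error at once. This stands in part. A reader might infer that raw counts will certainly be used; the documents do not show that. They show a variable without a unit and an operational sentence that, followed as written, misleads. Relying on someone to notice is weaker than writing the unit down.

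Three larger readings are tempting and are not supported:
- **That the comparison with placebo or the primary result is biased four-fold.** The factor is the same in every arm and cancels at equal exposure. Symptom scores and hormones are measured at the clamps and do not use these counts.
- **That the rise is five-fold because clamp 2 may be postponed by 7 days.** This needs counting past the stated period. Sections 6.1, 6.3 and 9.11.2 say 4 weeks or 28 days, and 6.2.2 supplies capsules for 4 weeks.
- **That clamp 2 will be counted as a treatment episode.** Section 9.10 places clamp 2 at the end of the intervention phase, and the calendar ends dosing the day before. Section 9.8 says how long the sensor is worn, not what is counted. The fair statement is that exclusion is the likelier reading but is nowhere written. If the episode were counted, it would fall on completers in every arm and largely cancel between arms.

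The selected pre-clamp day is likewise not a baseline-only problem. Clamp 1 also precedes randomization, so the baseline selection is balanced across arms in expectation.

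**Conclusion.** The point holds in this limited form. As written, the within-arm comparison in 9.11.2 produces about a four-fold rise under no effect (4.0 on 28 days, 3.86 on 27). It would hide any true reduction smaller than about 75%. This assumes raw counts, a constant underlying rate and equally complete wear in both periods. The arm-to-arm comparison is unaffected at equal exposure and shifts by roughly 4-11% of an arm mean for one early removal between days 21 and 7. The window limits at the clamps are secondary: small beside the unit problem, dependent on how several sections are read together, and worth settling in the same edit. This should be fixed before the data are analyzed; it does not threaten the trial's primary conclusions.

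**What to change.** In 9.11.2 and section 10:

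1. Define the variable as episodes per 7 days of valid CGM wear, in both periods. The null ratio becomes (4r/4)/(r/1) = 1.0 for any weekly rate r.
2. Compare arms on the on-treatment rate adjusted for the baseline rate, for example by ANCOVA. A plain difference is noisier, because a 7-day rate has 28/7 = 4 times the Poisson variance of a 28-day rate. Any within-arm change that is kept should use the same rate scale.
3. State the start and end of both windows. Put the hypoglycemia induced at clamp 2 explicitly outside the treatment window. Handle the 24 hours before each clamp the same way in both periods; dropping them from both avoids the residual 1.125 that remains if both are kept. Include withdrawn participants' wear time up to removal. A rate corrects for shorter exposure but not for removal that is itself related to hypoglycemia.

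**Cost.** Wording in two sections, slight extra programming and, if the pre-clamp 24 hours are dropped, about a day of CGM data per clamp. Should 4.1 govern, a 7-day baseline becomes 6 days, which raises the Poisson variance of the baseline rate by 7/6 − 1 = 17%.

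**Separately,** reconcile the CGM start: one week before clamp 1 in 4.1, 14 days in 9.11.2, week −2 in the calendar. The 7-day baseline fits any of these, so the ratios above do not change.

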1.2 Secondary Objectives and Endpoints

- To investigate whether carvedilol treatment reduces the amount of time T1DM patients with hypoglycemia unawareness spend in the hypoglycemic range as assessed by blinded CGM.
- To investigate whether carvedilol reduces the fear of hypoglycemia.

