
prompts behavioral defenses such as eating) responses to subsequent bouts of hypoglycemia¹¹⁻¹⁴. Thus begins the vicious cycle of recurrent hypoglycemia (RH) where hypoglycemia leads to further impairment of counterregulatory responses which in turn, begets more hypoglycemia and so forth. Because of the imperfections of current insulin therapies, those patients attempting to achieve glycemic control suffer an untold number of asymptomatic hypoglycemic episodes. Current estimates of symptomatic hypoglycemic episodes range from 2-3 incidences per week on average and severe, debilitating episodes occur once or twice each year. Therefore, developing therapies to prevent or eliminate hypoglycemia is of great importance.

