6.3 Duration of Therapy

The period of treatment is 4 weeks (28 days).

Subjects will be withdrawn or discontinued from the study if any of the following occurs:

- The subject withdraws consent for further participation in the clinical trial. At any time during the trial and without the need to provide a reason or rationale, a subject may choose to decline to participate further in the study. The subject will not suffer any consequences as a result.
- Subject is lost to follow-up despite efforts to contact them.
- Episodes of severe bradycardia and hypotension requiring hospitalization.

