9.10 The Clamp Procedure

Patients will be asked to reduce the dose of long-acting insulin 24 hours prior to the clamp study if applicable. The night before the clamp study, the subjects will be admitted into the CSC and the CGMs will be checked for hypoglycemia (reading <75-80mg/dl). We are setting this cut-off a little higher than the clinical definition of hypoglycemia (<70mg/dL) to ensure central mechanisms that are normally triggered by mild hypoglycemia are not activated⁷⁵. If hypoglycemia (<75-80mg/dL) is noted within 24 hours of beginning the clamp study, then the study will be delayed for one week. Qualifying subjects will be provided with a standardized low glycemic index meal to avoid fluctuations in blood glucose levels during the overnight fast. The CSC nursing staff will introduce an intravenous (antecubital vein) insulin drip in the subject and blood glucose levels will be maintained between 90-120mg/dl during the overnight fasting period. Blood glucose concentrations will be determined from a fingerstick using a point-of-care glucometer in order to titrate the insulin drip.

First Hypoglycemic Clamp: The next day, the patient will be asked to void their bladder prior to the start of the clamping procedure. The participant will then remain in bed in a supine position for the procedure. The participant will be asked to refrain from watching television during the procedure. A second catheter will be inserted into the contralateral hand vein for blood sampling and the sampling hand placed into a heated (~55°C) box to arterialize the blood. An ECG will also be connected to the subject to monitor heart electrical activity. Heart rate, blood pressure and ECG will be monitored every 15 minutes throughout the study. Prior to the drawing of each blood sample, the deadspace volume (~5-6ml) will be withdrawn into a syringe. A new syringe will be replaced onto the luer lock and the required blood volume drawn into new syringe. Following blood collection, the collected deadspace volume will be reinfused, followed by a saline infusion through the intravenous line to clear it of residual blood. Baseline blood samples (30mL) will be

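### The secondary objective is time spent in the hypoglycemic range, but the CGM analysis names episode number, duration and depth, and leaves duration and depth without a defined summary

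*Combined protocol and SAP*

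**What the plan says.** Three places describe the CGM outcome, and they do not match.

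- **Section 1.2 (secondary objectives)** asks whether carvedilol "reduces the amount of time T1DM patients with hypoglycemia unawareness spend in the hypoglycemic range as assessed by blinded CGM". This is a total per patient, and it is zero for a patient with no lows.
- **Section 9.11.2** opens with the frequency of episodes and compares the treatment period with "the number of hypoglycemic episodes encountered during the 7-day period before the first clamp study". It then adds: "Analysis of the CGM data will emphasize the number of hypoglycemic episodes as well as the duration and depth of the hypoglycemic episodes". The definition begins "A single hypoglycemic episode is defined as a glucose reading <70 mg/dL, followed by a reading ≥ 70 mg/dL, lasting at least 15 minutes", offers as an alternative at least two readings below 70 mg/dL over 15 minutes, and merges episodes less than 30 minutes apart.
- **Section 10** lists one secondary variable, the frequency of hypoglycemia by CGM, to be analysed by ANOVA.

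No section says whether duration and depth are means per episode, totals per patient or something else. None says what value a patient with no episode receives.

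**The concern.** The question posed in section 1.2 is not answered by any outcome named for analysis. Frequency does not measure time: a patient can have fewer but longer lows.

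Duration and depth could fill the gap, but the text ties them to the episodes and lists them apart from the number, which points to a per-episode summary. Such a summary has two weaknesses. It does not exist for a patient without an episode, so a change from baseline cannot be formed for someone with a clean baseline week. It also describes only the episodes that remain. If treatment removes the mildest ones, the average of the rest can stand still or look worse while the patient has less hypoglycemia.

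Because the summary is left open, it could also be chosen after the data are seen.

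**Working it through.** The plan gives no figure for duration, depth or time below 70 mg/dL, so there is nothing to reproduce. The checks below show how much the choice of summary could matter.

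**1. Patients with no value**

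Inputs: a 7-day baseline (section 9.11.2), 28 days of treatment (section 6.3) and 21 patients (section 4.3). The only rate in the documents is in section 2: "Current estimates of symptomatic hypoglycemic episodes range from 2-3 incidences per week on average". It refers to symptomatic episodes, so using it for CGM episodes is an assumption. A higher range of 5 to 7 per week is assumed alongside it.

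With m the expected count in the window, P(no episode) = exp(−m) under Poisson. With between-patient spread it is (1 + m/k)^(−k), a negative binomial with k = 2 assumed.

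| Rate per week | 7 days, Poisson | 7 days, k = 2 | 28 days, Poisson | 28 days, k = 2 |
|---|---|---|---|---|
| 2 | exp(−2) = 13.5% | 25% | exp(−8) = 0.03% | (1+4)^(−2) = 4% |
| 3 | exp(−3) = 5.0% | 16% | exp(−12), below 0.01% | (1+6)^(−2) = 2% |
| 5 | exp(−5) = 0.7% | 8% | negligible | (1+10)^(−2) = 0.8% |
| 7 | exp(−7) = 0.1% | 5% | negligible | (1+14)^(−2) = 0.4% |

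At 2 to 3 per week, Poisson gives 21 × 0.135 = 2.8 down to 21 × 0.050 = 1.0 patients without a baseline value. Section 9.10 adds a little: "If hypoglycemia (<75-80mg/dL) is noted within 24 hours of beginning the clamp study, then the study will be delayed for one week". The last day before a clamp is therefore free of episodes, and about six of the seven days can contain one: exp(−12/7) = 18.0% and exp(−18/7) = 7.6%.

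If treatment halved the rate of 2 to 3 per week, the 28-day share would be at most exp(−4) = 1.8% by Poisson, or (1+2)^(−2) = 11% to (1+3)^(−2) = 6% with k = 2.

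**2. Dependence on which episodes remain**

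Simple example, all figures assumed. A mild episode lasts 20 minutes with nadir 65 mg/dL; a severe one lasts 60 minutes with nadir 50 mg/dL.

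| | Episodes | Total minutes | Mean duration (min) | Mean nadir (mg/dL) |
|---|---|---|---|---|
| Before: 8 mild, 4 severe | 12 | 160 + 240 = 400 | 33.3 | (520 + 200)/12 = 60.0 |
| After: 4 mild, 4 severe | 8 | 80 + 240 = 320 | 40.0 | (260 + 200)/8 = 57.5 |
| Both kinds halved: 4 mild, 2 severe | 6 | 80 + 120 = 200 | 33.3 | 60.0 |

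In the second row total time falls 20% and both averages look worse. In the third, total time halves and neither average moves.

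Distributional version, also assumed: depth D below 70 mg/dL is gamma with mean 10, and treatment lifts every nadir by 5 mg/dL. The episode ratio is P(D > 5), the total-depth ratio is E[(D − 5)+]/10, and the mean-depth ratio is the second divided by the first.

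| Gamma shape | Episodes | Total depth | Mean depth per episode |
|---|---|---|---|
| 0.5 (more skewed) | 0.48 | 0.68 | 1.42 |
| 1 (exponential) | 0.61 | 0.61 | 1.00 |
| 2 (less skewed) | 0.74 | 0.55 | 0.75 |

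Duration can behave in the same way. If time beyond 15 minutes is exponential with mean 30, shortening every low by 15 minutes removes 1 − exp(−0.5) = 39% of episodes and leaves the mean at 45 minutes. This example ignores the two-reading alternative and the merging rule.

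**3. Power**

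Simulations used 7 placebo against 14 treated patients, 28 days, 3 to 5 episodes per week, k = 2 to 4 and the same 5 mg/dL lift. With exponential depths, mean depth per episode is significant in about 3% to 5% of runs (no signal) and the daily total in about 24% to 40%. With shape 2 the order reverses: about 45% to 74% per episode against 30% to 54% for the total.

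**The case against.** The best defence is that the plan nowhere says average. If duration means total time per patient, a patient with no episode scores zero and losing mild episodes lowers the total. That is correct, and per-episode averaging must be treated as a reading, not as the plan's stated method. It does not close the gap. Depth still has no value without an episode. Summed episode duration is also not quite time below 70 mg/dL, because lows too short to count are left out.

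A second defence is that duration and depth are supporting descriptors: section 10 lists frequency, which is defined at zero, and the sentence in section 9.11.2 that plans comparisons comes before duration and depth are mentioned. A fall in episode count would be reported beside any flat average. This stands and limits the weight of the point, but frequency is not the quantity in section 1.2.

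A reader might infer that the best responders would be dropped and randomization broken by missing values. The documents do not support that. Most patients without a value would lack it in the baseline week, before randomization (section 4.1), where the cost is a lost change score and not selection by treatment. Nor can the section 2 rate be taken as a CGM rate: the same section refers to uncounted asymptomatic episodes, and blinded CGM in unaware patients may record more.

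A reader might also infer that a working drug would look harmful. That occurs at shape 0.5 and not at shape 2, and nothing in the documents selects a shape.

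**Conclusion.** The point holds in a limited form. What is certain from the text is that section 1.2 sets time in the hypoglycemic range as the objective, that neither section 9.11.2 nor section 10 names it as an outcome, and that duration and depth have neither a summary nor a zero-episode rule.

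What is conditional is the harm. On the per-episode reading, roughly 1 to 3 of 21 patients would lack a baseline value at 2 to 3 episodes per week by Poisson, and fewer than one at 5 to 7. With k = 2 the expected numbers are higher: 21 × 0.25 = 5.3 to 21 × 0.16 = 3.4, and 21 × 0.082 = 1.7 to 21 × 0.049 = 1.0. Per-episode averages can miss or reverse a real fall in hypoglycemia, with size and direction set by an unknown depth distribution.

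This concerns secondary outcomes in a small trial and leaves the primary outcomes untouched. It should be settled before the CGM data are analysed.

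**What to change.** In sections 9.11.2 and 10, name as secondary outcomes compared between arms, alongside episode frequency:

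- minutes below 70 mg/dL per 24 hours of valid CGM time, which is the section 1.2 objective;
- area below 70 mg/dL (mg/dL × minutes) per 24 hours of valid CGM time, as the depth measure defined for every patient.

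State that a patient with valid CGM data and no reading below 70 mg/dL scores zero on both. Report duration and depth per episode as description only, with the number of patients contributing in each arm and period.

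The cost is wording and a different summary of CGM data that will be exported anyway. There is a small downside: totals mix frequency with severity, and they can have less power than per-episode means if depths are not very skewed. Keeping the descriptive per-episode table beside the totals lets a reader separate the two.
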